9.3 Reporting Procedures

9.3.1 Serious Adverse Events

All SAEs must be documented and reported to IVAC or its designate, even if the investigator considers that the SAE is not related to treatment. The study clinician will complete a **Serious Adverse Event Form** within the following timelines of such events:

- All deaths and immediately life-threatening events, whether related or unrelated, will be recorded on the Serious Adverse Event Form and sent by fax or email within 24 hours of site awareness.
- SAEs other than death and immediately life-threatening events (i.e., events resulting in hospitalization or prolongation of hospitalization, persistent or significant disability or incapacity, or other significant events determined by the investigator to be SAEs), regardless of relationship, will be reported via fax or email by the site within 48 hours of becoming aware of the event.

IVAC will be primarily responsible for medical monitoring of serious adverse events documented by the investigator. Medical Officers from PATH serving as technical consultants will review all serious adverse events and provide guidance regarding SAE management, including classification and reporting. Details for review of serious adverse events and other unanticipated problems will be in an SOP drafted prior to study initiation.

9.3.2 Reporting of AEs

Collected SAEs and AEs will be reported to responsible ethical review committees according to their

requested timelines. An SOP for reporting to the responsible committees will be developed with reporting requirements and timelines prior to study initiation. It will be the investigator's responsibility to assure that all reportable events are reported to the proper authority, or to IVAC, and/or its designate in a timely manner and according to existing SOP. PATH technical consultants may assist the investigator with regulatory reporting, per the finalized SOP.

9.3.3 Other Unexpected Issues/Unanticipated Problems

During study process, if there are any problems related to the trial (unanticipated problems), the Principal Investigator is responsible for reporting to IVAC and PATH to discuss reasonable ways of handling the problem. The Principal Investigator is responsible for reporting any unanticipated problems that affect the health, welfare, or rights of study participants, or that may impact the integrity of the study data to the ethics committees involved in the review of the research. The Principal Investigator should maintain written documentation of all unanticipated problems, their reporting, and resolution.

9.3.4 Reporting of Pregnancy

All pregnancies detected among women enrolled in the trial who receive at least one injection of study product must be reported on a pregnancy report CRF. All pregnancies must be followed to term and outcome reported to IVAC and regulatory agencies. Unblinding of allocation of treatment of female subjects who become pregnant will not occur until after study completion, unless medically indicated.

9.4 Duration of Follow Up for AE Resolution

All reported AEs should be followed until resolution or stabilization, or until the subject's participation in the study ends. Subjects who have an ongoing study product-related SAE at study completion or at discontinuation from the study will be followed by the PI, or his/her designee, until the event is resolved or determined to be irreversible, chronic, or stable by the PI.

9.5 Safety Oversight

9.5.1 Protocol Safety Review Team

Safety will be monitored daily during the active immunization Phase of the study by on site clinical staff, and routinely by the Medical Officer at PATH and designated pharmacovigilance medical officer from a CRO.

9.5.2 Data and Safety Monitoring Board

A DSMB comprised of independent vaccine and infectious diseases experts and a biostatistician will (1) review the initial cohort of trial participants and advise on continuing with vaccinations for the rest of the study and (2) periodically review cumulative data. To allow for accurate assessment, the DSMB will

review reports that have been unblinded to the study code. Investigators and other persons associated with the conduct trial will remain blinded.

Initial Cohort Review:

After 300 subjects receive both vaccinations, further enrollment in the study will pause for approximately 6 months while the immunogenicity and safety data are compiled by the Data Management CRO and reviewed by the DSMB. Study enrollment will proceed if the DSMB advises continuation of the trial and the Vietnam Ministry of Health concurs.

Periodic Review:

The DSMB will conduct periodic review of (but will not be limited to): demographic information on study; interim/cumulative data for evidence of study-related AEs; discontinuations of study vaccinations; data quality, completeness, and timeliness; factors that might affect the study outcome or compromise the confidentiality of the trial data (such as treatment and endpoint unblinding); and, factors external to the study such as scientific or therapeutic developments that may impact participant safety or the ethics of the study.

The DSMB reviews will be summarized and contain recommendations to the study sponsor concerning whether or not there are safety concerns, if the study should continue without change or modified, or if it should be terminated. Decisions regarding permanent discontinuation of study product in individuals will be made by the PSRT based on careful review of all relevant data and by consulting with the DSMB, if necessary. Although it is not likely to happen, if the protocol team has serious safety concerns with the study and concludes the study product should no longer be administered and accrual into the protocol should stop, the team should request a review of the data by the DSMB. If, at any time, a decision is made to discontinue the study product for all participants, IVAC will notify the MOH and the site investigators of record will notify the responsible IRBs/IECs expeditiously.

DSMB recommendations will be carefully considered by the sponsor. If a disagreement arises between the sponsor and the DSMB, the sponsor will discuss it with the DSMB in order to reach consensus. If attempts to reach consensus fail, the sponsor's opinion will prevail. In such situation, the sponsor will inform the regulatory authorities.

All summary reports from the DSMB will be submitted to IRBs.

10 Monitoring

10.1 Monitoring Plan

Individuals qualified by education, training, and experience will carefully monitor the study. The study monitors will periodically contact the site and perform on-site visits. The extent, nature, and frequency of visits will be based on such considerations as study objectives, study design and complexity, and enrollment rate. Periodicity and nature of monitoring activities will be described in the Monitoring Plan that will be approved by IVAC in advance of monitoring. The Monitoring Plan will contain detailed

report requirements and study progress for IVAC. Representatives of IVAC or designates may participate in monitoring visits or visit the study site on their own in order to provide proper oversight.

10.2 Initiation Visit

The study monitor will contact the site prior to the start of the study to discuss the protocol and data collection procedures with site personnel. Prior to enrollment of subjects at the study site, specific regulatory documents must be available. These include approvals from the independent ethics committee (IEC) at the Vietnam Ministry of Health and from institutional review boards of the participating institutions. Curriculum vitae for key investigators must also be available. IVAC will inform the investigator of any additional documents that need to be provided.

10.3 Routine Monitoring Visits

Monitoring will be conducted according to an agreed upon Site Monitoring Plan. Monitoring will be targeted towards issues critical to the rights and welfare of study participants as well as accuracy and integrity of the study data. Individuals responsible for monitoring the study should have access to all records needed in order to periodically ensure the ethical and safe conduct of the study and the integrity/validity of the recorded data.

During sites visits and contacts, the monitor will:

1. Assess if consent was properly obtained.
2. Assess adherence to the protocol eligibility criteria.
3. Look for evidence that randomization was followed.
4. Look for evidence that blinding was maintained.
5. Look for evidence that the product was administered correctly.
6. Check on study conduct and documentation of procedures/assessments related to the study endpoints:
 - Specimens obtained correctly.
 - Specimens labeled correctly.
 - Reactogenicity diaries completed and collected.
7. Check on study conduct and documentation of protocol-required safety assessments, including SAEs.
8. Ensure that there is documentation of withdrawals and deaths with reasons provided.

As part of study conduct, the Principal Investigator agrees to allow the monitor direct access to all relevant documents and to allocate his/her time and the time of his/her staff to discuss findings and relevant issues. The study consent also makes participants aware that medical records relevant to events in the study may be accessed and viewed by people conducting and overseeing the study.

The Principal Investigator also agrees to allow representatives of IVAC or its designates to occasionally accompany the monitor during site visits.

10.4 Close-out Visit

Upon completion of the study, the study monitor and the investigator will conduct the following activities:

- Data clarification and/or resolution.
- Accounting, reconciliation, and destruction at sites of used and unused vaccines.
- Review of site study records for completeness.
- Return of all study data to IVAC.

11 Audits and Inspections

For the purpose of compliance with applicable regulatory guidelines, it might be necessary for IVAC, its designates, or national or foreign regulatory authorities to conduct a site audit. This could occur at any time from site initiation to after conclusion of the study.

The Principal Investigator agrees to allow the auditor to have direct access to all relevant documents and to allocate his/her time and the time of his/her staff to the auditor to discuss findings and any relevant issues.

National and foreign regulatory authorities may conduct a regulatory inspection of this study. If a regulatory authority requests an inspection, the Principal Investigator must inform IVAC immediately about this request. The Principal Investigator agrees to allow the inspector(s) direct access to all relevant documents and to allocate his/her time and the time of his/her staff to the inspector(s) to discuss findings and any relevant issues.

12 Statistical Considerations

12.1 Study Hypothesis

The study hypothesis is that two 0.5 mL doses of whole virion monovalent A/H5N1 influenza vaccine (IVACFLU-A/H5N1) adjuvanted with alum will be safe and well tolerated in healthy adults, and that at least one of the two doses tested will be immunogenic in 60% or more of the subjects tested.

12.2 Sample Size Considerations

This is an operational, seamless Phase 2/3 trial with a primary objective to evaluate the immunogenicity and safety of two dose levels of IVACFLU-A/H5N1, 15 mcg vs. 30 mcg (study Phase 2), and select the optimal of the two doses to evaluate further for potential licensure (study Phase 3). The sample size for this study was selected for the primary immunogenicity analysis and the safety analysis to satisfy the licensure requirements by the MOH. The sample size for Phase 2 of the study is approximately 300 subjects (100 per group), and for Phase 3, 1500 subjects (1000 for the IVACFLU-A/H5N1 group and 500 for the placebo group).

Overall, a total of approximately 1100 subjects will receive the selected dose of study vaccine, which will allow for the recognition of SAEs occurring at a frequency of less than one percent. The probability of observing at least one vaccine-related serious adverse event among 1100 subjects is greater than 90 percent if the true rate of such events is 0.21 percent. If no vaccine-related serious adverse events are observed in 1100 vaccinees receiving IVACFLU-A/H5N1, this would represent an upper bound of the two-sided 95 percent Confidence Interval (CI) on the percentage of such events of 0.3 percent.

Sample Size	No. of Events	Exact Two-Sided 95% CI
N=1100	0 events	[0.0%, 0.33%]
	1 event	[<0.01%, 0.51%]
	2 events	[0.02%, 0.65%]
	5 events	[0.15%, 1.06%]
	10 events	[0.44%, 1.67%]

12.3 Immunogenicity

The sample size calculations for the primary immunogenicity endpoints for Phase 3 are based on the following acceptance criteria:

- Percentage of subjects achieving HAI titer ≥ 40 on 21 days post-dose two should meet or exceed 60%.

For the Phase 2 dose selection component (Phase 2), samples from approximately 100 subjects per IVACFLU-A/H5N1 dose level will be tested by HAI and MNT assay. Phase 2 of this study is designed to provide 80% power to detect a 20 percentage points difference in response rates between the two dose groups (e.g. 50% for the 15 mcg dose vs. 70% for the 30 mcg dose). The minimum statistical difference that can be detected at two-sided 5% alpha is approximately 14 percentage points between the two dose groups (e.g. 50% for the 15 mcg dose vs. 64% for the 30 mcg dose). The selection of the dose for the Phase 3 will be based on multiple immunogenicity endpoints as listed in the primary and secondary immunogenicity endpoints. The power calculations were estimated based on the two-sided 0.05 Z test with unpooled variance using PASS 13.

For the Phase 3 component, samples from approximately 300 subjects receiving the IVACFLU-A/H5N1 (vaccinees) will be tested by HAI for the analysis of the immunogenicity endpoint. MN testing for the Phase 3 will be determined based on the results from Phase 2 and a determination that MN testing will add value to the Phase 3 study. The table below provides exact two-sided 95% CIs for either endpoints for different observed response rates for 300 evaluable subjects. This study is designed to provide the precision of the immune responses as estimated by the width of the confidence intervals less than ± 5.8 percentage points around the range of expected rates.

Observed Seroresponse Rate	Percentage of Subjects	Exact two-sided 95% CI
300/300	100%	[98.8%, 100%]
270/300	90.0%	[86.0%, 93.2%]
240/300	80.0%	[75.0%, 84.4%]
210/300	70.0%	[64.5%, 75.1%]

Observed Seroresponse Rate	Percentage of Subjects	Exact two-sided 95% CI
180/300	60.0%	[54.2%, 65.6%]
150/300	50.0%	[44.2%, 55.8%]

Also, this study with 300 evaluable subjects is designed to provide 97% and >99% probability to demonstrate adequate immune responses, $\geq 60\%$ achieving post-dose two HAI titer 1:40, if the true percentages of subjects achieving seroprotective level are 65% and 70%, respectively.

12.4 Endpoints and Minimum Significant Differences

12.4.1 Definition of Analysis Sets

Definitions of Populations to be Analyzed:

Enrolled Population

All screened subjects who provide informed consent, regardless of the subject's randomization and treatment status in the trial.

Full Analysis (FA) Population

All subjects in the enrolled population who were randomized, received a study vaccination. This population will serve as the primary analysis population for all safety objectives. The analysis based on this population will serve as the supportive results for all immunogenicity objectives. Subjects will be analyzed as received.

Per Protocol (PP) Population

All subjects in the Full Analysis population who have valid post-vaccination immunogenicity measures with no major protocol violations that are determined to potentially interfere with the immunogenicity assessment of the study vaccine. This population will serve as the primary analysis population for all immunogenicity objectives.

The criteria for exclusion of subjects from the Per Protocol Population will be established before breaking the blind and will be based on the blinded review of protocol violations.

12.4.2 Analysis of Safety Endpoints

The safety profile of IVACFLU-A/H5N1 will be evaluated by the number and the proportion of subjects experiencing AEs, related or not related, of the following five categories for all subjects and by age group (18-40 years of age and 41-60 years age):

- Number and percentage of subjects with solicited local and systemic adverse events within 30 minutes after each vaccination.
- Number and percentages of subjects with solicited local adverse events (redness, swelling, pain, induration, and tenderness) over a 7-day period (Days 1-7; Days 22-28) post each vaccination.

- Number and percentages of subjects with solicited systemic/general adverse events (fever, fatigue/malaise, muscle aches (generalized), joint aches, chills, nausea, vomiting, and headache) over a 7-day period (Days 1-7; Days 22-28) post each vaccination.
- Number and percentages of subjects with unsolicited adverse events for 21 days post each vaccination.
- All serious adverse events (SAEs) occurring over the entire study period. (Days 1-91).

Counts of all events will be reported and summarized according to event severity as “any local AE”, or “any systemic AE”, and by relationship to administration of study product, as deemed by a blinded study clinician. Percentages of subjects experiencing each reaction or event, or at least one reaction or event, will be calculated along with two-sided exact 95% CIs. For the solicited local and systemic/general adverse events, Fisher’s exact test for two proportions or Chi-squared test severity grade categories at 2-sided 0.05 alpha without a multiplicity adjustment will be used to compare the treatment groups as an initial screening step rather than formal statistical hypothesis testing for further clinical evaluation. No statistical testing will be performed for unsolicited AEs including SAEs.

12.4.3 Analysis of Immunogenicity Endpoints

Immune responses to IVACFLU-A/H5N1 will be evaluated by the following for all subjects in the immunology subset and by age group (18-40 years of age and 41-60 years age):

Phase 2 (all 300 subjects)

- Percentage of subjects with a serum HAI titer $\geq 1:40$ on Day 22 and Day 43 (**Primary Endpoint**).
- Percentage of subjects achieving a seroresponse (at least a four-fold increase in post-vaccination titer) on Day 22 and Day 43 as determined by HAI.
- Percentage of subjects with at least a four-fold rise in titer at Day 22 and 43, as determined by MN.
- Geometric Mean Titer (GMT) of Day 22 and Day 43 as determined by the HAI and MN tests.
- Geometric Mean Titer Ratio (GMTR) of Day 22/Day 1 and Day 43/Day 1 as determined by the HAI and MN tests.

Phase 3 (approximately 300 vaccinee subjects for HAI; MN testing to be determined on the results of Phase 2)

- Percentage of subjects with a serum HAI titer $\geq 1:40$ on Day 43 (**Primary Endpoint**).
- Percentage of subjects achieving a seroresponse (at least a four-fold increase in post-vaccination titer) on Day 43 as determined by HAI.
- Percentage of subjects with at least a four-fold rise in titer at Day 43, as determined by MN*.
- Geometric Mean Titer (GMT) of Day 43 as determined by the HAI and MN* tests.
- Geometric Mean Titer Ratio (GMTR) of Day 43/Day 1 as determined by the HAI and MN* tests.

* MN tests and associated endpoints will be conducted on Phase 3 vaccinees based on results from Phase 2 and a decision that MN testing will add value to the study.

Percentages of subjects with immune response will be calculated along the corresponding two-sided exact (Clopper-Pearson) binomial CIs. GMT and GMTR will be summarized by treatment group along with the corresponding two-sided 95% CIs, by exponentiating the corresponding log-transformed means and their 95% CIs. Titers below the lowest limit of quantitation (i.e., below the starting dilution of assay reported as “< 10”) will be set to half that limit (i.e., $10 / 2 = 5$). For Phase 2, two-sided 95% CIs for the difference in proportions of participants demonstrating seroresponse between the two dose groups will be based on the Newcombe hybrid score (METHOD=SCORE riskdiff-option for PROC FREQ in SAS). For the GMT and GMFR, two-sided 95% confidence intervals (95% CIs) for the ratios post-vaccination GMTs/GMFRs between two dose groups will be constructed using a log-normal distribution. The log values will be used to construct a 95% CI using t-distribution for the mean difference between the two treatment groups. Then the mean difference and the corresponding 95% CI limits will be exponentiated to obtain the GMT ratio and the corresponding CI. No comparisons will be made between the IVACFLU-A/H5N1 dose groups and the placebo group in both Phase 2 and Phase 3.

This study has a single primary endpoint and it maintains the experiment-wise Type I error rate at 2-sided of 0.05. No multiplicity adjustment to the error rate, alpha, will be made for secondary immunogenicity endpoints. Also no imputation of missing immunogenicity measures will be made.

13 Data Capture Methods

CRFs will be developed and data will be managed to the extent possible in accordance with internationally agreed-upon standards, such as the Clinical Data Acquisition Standards Harmonization, which defines basic standards for the collection of clinical trial data, and/or The Society for Clinical Data Management’s Good Clinical Data Management Guidelines.

All the information required by the study protocol must be recorded on the CRF provided by the sponsor, or if it is laboratory assay data, transferred in a format agreeable to the sponsor. All data must be entered legibly, as described in any *CRF Completion Guidelines*. An explanation must be provided for any missing data. Data entered onto the CRFs must be accurate, legible, contemporaneous, original (or traceable to the original source), and attributable.

All source documents and CRFs should be completed in a neat, legible manner to ensure accurate interpretation of data. Black ink is required to ensure clarity of reproduced copies. When making changes or corrections, study staffs are to cross out the original entry with a single line, and initial and date the change. Do not erase, overwrite, or use correction fluid or tape on the original. All source documents and laboratory reports must be reviewed by the clinical and laboratory teams, who will ensure that they are accurate and complete.

The investigator must sign and date each CRF or batch of CRFs, attesting to his responsibility for the quality of all data recorded and that the data represent a complete and accurate record of each subject’s participation in the study.

Clinical safety data will be entered onto study CRFs from laboratory report forms. Visit dates and laboratory procedure dates will be recorded on all forms. All participants will be assigned a unique

screening number and subject identification number at study enrollment – this study participant number will be included on all forms and in the trial database and will serve to link study data to specific individuals. CRFs will be entered, verified for accuracy, linked by study participant number, and managed using database management software with proper security, controls, and the ability to identify who is entering or making changes to the data in the system.

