4.2 Study Sites

Phase 2 of this study will be conducted at one clinical site in one province and Phase 3 will be conducted in three provinces in Vietnam.

Phase 2

The Phase 2 part of this study will be conducted in the Khanh Hoa Province at Ninh Hoa District Health Center. Data entry/CRF storage will be at the Khanh Hoa Provincial Health Department.

Phase 3

The Phase 3 part of the study will be conducted at three provinces, as follows:

1. Khanh Hoa Province: (same site as Phase 2, but study activities move to the communes)
 - Study activities at the Ninh Da, Ninh Binh, and Ninh Quang Commune health centers.
 - Data entry/CRF storage at the Khanh Hoa Provincial Health Department.
2. Hai Phong Province:
 - Study activities at the Cap Tien, Kien Thiet, and Hung Thang Commune health centers.
 - Data entry/CRF storage at the Hai Phong Preventive Medicine Center.
3. Hoa Binh Province:
 - Study activities at the Hop Kim, Nam Thuong, and Thuong Bi Commune health centers.
 - Data entry/CRF storage at the Hoa Binh Preventive Medicine Center.

For Phase 3, study documents will be stored at the provincial level where data entry will occur, and will be moved to the particular commune health center when a study visit is occurring there.

These locations were satellite sites for several vaccine clinical trials conducted in collaboration with National institute of Hygiene and Epidemiology (NIHE). The staff of the district health center, as well as the staff of the provincial centers in the three provinces have experience in implementing vaccine trials and observational studies on various infectious diseases. They also have experience in working with contract research organizations (CROs), and with local and international sponsors.

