5.4 Treatment Assignment Procedures

5.4.1 Randomized Procedure

This is a double-blind, randomized, and controlled trial with a 1:1:1 ratio among three groups in Phase 2: 15 mcg/mL vaccine, 30 mcg/mL vaccine, and placebo; and 2:1 ratio between two groups in Phase 3: either 15 mcg/mL or 30 mcg/mL vaccine and placebo. Each subject will be assigned a unique screening number by the investigator after signing the informed consent.

The Investigator will maintain the screening/enrollment log. The log will contain essential information including subject name, date of screening, gender, date of birth, whether or not the subject meets eligibility criteria, whether subject is enrolled and date, and if not enrolled, reason why the subject is not enrolled or not randomized.

Once a subject identification number has been assigned to a subject, it will not be used again. Additional subjects may be randomized into the study at the discretion of the sponsor in the case of any subject who is randomized but does not receive any study vaccine.

The permuted randomization block design procedure will be used to generate the randomization schedules for both Phase 2 and Phase 3. The randomization will be stratified by province and age group (18-40 years of age and 41-60 years age). The block size for each part will be chosen based on the number of treatment groups and anticipated enrollment sizes at each province.

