For each percentage of subjects with defined immune response endpoints, the percentage and its corresponding 2-sided exact (Clopper-Pearson) binomial 95% confidence interval (95% CI) around the percentage will be computed for each treatment group.

In addition, to compare HAI and MN test seroresponse, individually, between the two dose groups, two-sided 95% CIs for the difference in the percentages of participants demonstrating seroresponse between the two dose groups will be provided for each time-point (Day 22 and Day 43) based on the Newcombe hybrid score (Newcombe, 1998)⁴.

Geometric Mean Titers (GMTs):

- Geometric Mean Titer (GMT) of Day 22 and Day 43 as determined by the HAI and MN tests.
- Geometric Mean Fold Rise (GMFR): Geometric Mean of Titer Ratio of Day 22/Day 1 and Day 43/Day 1 as determined by the HAI and MN tests.

GMT along with the corresponding two-sided 95% CIs, by exponentiating the corresponding log-transformed means and their 95% CIs, will be summarized by treatment group, the HAI and MN tests, and each time-point (Day1, Day 22 and Day 43). The same approach will be used to summarize GMFR separately by treatment group, Day 22/Day 1 and Day 43/Day1, and the HAI and MN tests.

Furthermore, to compare two dose groups based on GMT endpoints, two-sided 95% CIs for the ratios post-vaccination GMT between two dose groups will be constructed using a log-normal distribution, separately for Day 22 and Day 43 and the HAI and MN tests. The log values will be used to construct a 95% CI using t-distribution for the mean difference between the two dose groups. Then the mean difference and the corresponding 95% CI limits will be exponentiated to obtain the GMT ratio and the corresponding CI. The same approach will be used to compare two dose groups based on GMFRs

³ Note that this endpoint is expected to be equivalent to another commonly used endpoint of seroconversion as defined as a post-vaccination titer $\geq 1:40$ if baseline titer $< 1:10$ OR significant increase in antibody titer post vaccination (at least a four-fold increase from baseline titer) if baseline titer is $\geq 1:10$, since all subjects are expected to have baseline titer of $< 1:10$. If at least one subject has baseline titer $\geq 1:10$, an additional endpoint of seroconversion as defined above will also be analyzed

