For the solicited local and systemic/general adverse events, Fisher's exact test for two proportions or the Cochran-Mantel-Haenszel test⁵ for severity grade categories at 2-sided 0.05 alpha will be used to compare the treatment groups. No formal hypothesis testing with multiplicity adjustment will be performed. Furthermore, no statistical testing will be performed for unsolicited AEs including SAEs.

In addition, subject listings of adverse events will include details such as the following: MedDRA codes, study day of onset, seriousness, duration, action/treatment, outcome, severity, relatedness, and current status. Concomitant medications will also be coded and listed.

Furthermore, additional analyses will be repeated by combining safety outcomes of the selected dose group and placebo group from both Phases 2 and 3 cohorts if needed.

⁵ The Cochran-Mantel-Haenszel test is better method for comparing severity grade categories than the Chi-squared test as proposed in the study protocol

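### Phase 2 dose comparisons leave out age group, the only working randomisation stratum in that phase: a free but small gain in precision (minor)

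*Protocol*

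**What the plan says.** Protocol 5.4.1: "The randomization will be stratified by province and age group", the age groups being 18-40 and 41-60 years. Protocol 4.2 limits the working strata in the first stage: "Phase 2 of this study will be conducted at one clinical site in one province".

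Protocol 12.4.3 and section VII of the interim SAP give the Phase 2 dose comparisons. For the difference in response proportions, the interval "will be based on the Newcombe hybrid score", with no strata named. For GMT and GMFR ratios the interim SAP says "The log values will be used to construct a 95% CI using t-distribution for the mean difference between the two dose groups", with no age term.

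For solicited adverse events, section VIII of both SAPs gives Fisher's "exact test for two proportions or the Cochran-Mantel-Haenszel test", the latter for severity grades. Neither SAP names strata for it. A footnote in the final SAP explains the choice only as better suited to severity grades than the chi-squared test in the protocol.

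Age group does appear in the analysis, but as a separate set of results for each age group. It is not used to form a pooled, stratified comparison.

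**The concern.** When arms are balanced within age groups by design, the variation in response between age groups largely cancels out of the dose difference. An interval that ignores age still counts that variation as noise, so it is somewhat wider than the design requires whenever response depends on age. The information is on file for every subject.

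The Phase 2 comparison is a close one. The dose-selection table (Protocol 3.2.1, interim SAP IX) has a 13-point cut-off, and the 95% half-width for the difference is also about 13 points. Precision that costs nothing is therefore worth having. On the safety side, leaving the Cochran-Mantel-Haenszel strata unstated lets the programmer choose none, age, province or both.

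**Working it through.** **Inputs from the documents.** 100 per group (Protocol 12.2); 50% versus 70% response, two-sided 5% level, unpooled Z test (Protocol 12.3).

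**Assumptions, because the documents give no figure.** Half of the subjects fall in each age group (w = 0.5), and the age gap g in response is the same in both dose groups. A range of g is shown.

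**Reproducing the plan's figures.** Protocol 12.3 says "Phase 2 of this study is designed to provide 80% power to detect a 20 percentage points difference".
- Standard error = sqrt(0.50×0.50/100 + 0.70×0.30/100) = sqrt(0.0046) = 0.0678.
- Power without continuity correction = Φ(0.20/0.0678 − 1.96) = 83.9%.
- Power with continuity correction = Φ(0.19/0.0678 − 1.96) = 80.0%, which matches the plan.
- The plan's smallest significant difference of about 14 points also reproduces: from 50%, Z reaches 1.96 at 13.6 points.

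**Effect of stratifying by age.** The within-stratum variance in each arm is p(1−p) − w(1−w)g². For g = 0.20 the variance of the difference is (0.25 − 0.01)/100 + (0.21 − 0.01)/100 = 0.0044, so the half-width is 1.96×sqrt(0.0044) = 13.00 points, against 1.96×sqrt(0.0046) = 13.29 unstratified.

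| Age gap (points) | Half-width, unstratified | Half-width, age-stratified | Power by formula, stratified (unstratified 83.9%) |
|---|---|---|---|
| 0 | 13.29 | 13.29 | 83.9% |
| 10 | 13.29 | 13.22 | 84.3% |
| 20 | 13.29 | 13.00 | 85.4% |
| 30 | 13.29 | 12.63 | 87.4% |
| 40 | 13.29 | 12.08 | 90.1% |

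A 70/30 age split gives slightly less: 13.05 points and 85.2% at a 20-point gap. Both half-width columns use the simple normal formula so that like is compared with like.

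**Validity of the planned interval.** The Newcombe interval was simulated 400,000 times per setting with arms exactly balanced on age.
- Coverage at 50% versus 70% was 95.1%, 95.1%, 95.5%, 96.1% and 96.9% for gaps of 0, 10, 20, 30 and 40 points.
- With both doses at 60%, it excluded zero in 5.2%, 5.0%, 4.7%, 4.0% and 3.3% of trials.
- Simulated power at a 20-point gap was 83.7% for the planned interval and 84.5% for a stratified normal interval. At a 30-point gap it was 84.4% and 86.9%. The real gain in power is thus a little smaller than the formula column suggests, because balanced allocation already helps the unstratified analysis.

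**Log titre.** With an assumed within-stratum SD of 1.7 log2 units and a 1 log2 difference between equal age strata, the between-age variance is 0.5×0.5×1² = 0.25. The variance reduction is 0.25/(1.7² + 0.25) = 0.25/3.14 = 8.0%, or about 4% in interval width.

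**Safety, Phase 3.** Take 500 versus 100 (final SAP preface), the Phase 1 rates of any solicited event at 15 mcg and placebo, 81.3% and 33.3% (Protocol 2.1.3, Table 5), and an assumed 20-point gap between two equal strata. The half-width of the difference goes from 9.85 to 9.61 points.

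**The case against.** The strongest reply is that the plan is valid as written and the gain is too small to matter. Most of that stands.

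- A reader might infer that the unstratified interval threatens the dose choice. It does not. The selection table uses observed percentages and a 13-point observed difference, and no interval enters it. Stratified allocation also keeps crude and stratified estimates close: a 51% versus 49% age mix with a 20-point gap moves the difference by 0.02×20 = 0.4 points. The interim SAP also weighs secondary immunogenicity endpoints, so the GMT ratio intervals may inform judgement, but no threshold is attached to them.
- A reader might infer that two strata are ignored in the dose comparison. Phase 2 has one province, so only a two-level age factor remains.
- A reader might infer that the Cochran-Mantel-Haenszel test is shown to ignore the strata. The SAPs leave its strata unstated, which is a gap in specification. Only Fisher's test is plainly unstratified. Both are described as screening for clinical follow-up, and unsolicited and serious events are not tested.
- With 100 placebo subjects over two sites and two age groups (final SAP), strata average 25 placebo subjects, so an exact test remains sensible for infrequent reactions.
- The size of the gain rests on assumed age gaps. Phase 1 subjects were aged 18 to 30, so the programme's own data do not inform it.
- The final SAP reports 15 mcg as already selected. From that point a changed Phase 2 comparison would be post hoc.

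What survives is that the randomisation strata are known for everyone, are used in no named comparison, and can be used without new data.

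**Conclusion.** This is a minor, free improvement and not an error. The Phase 2 risk difference and the GMT and GMFR ratios omit age group although allocation was stratified on it. At 50% versus 70%, with equal age strata and the same age gap in both arms, using it narrows the half-width by 0.07, 0.29 or 0.66 points for age gaps of 10, 20 or 30 points, and by nothing if response does not vary with age. The planned interval keeps its coverage and does not inflate the type I error; it becomes mildly conservative as the age gap grows. No planned conclusion is shown to change: the dose table does not use intervals, and neither phase compares vaccine with placebo on immunogenicity. For safety, the supportable criticism is that the Cochran-Mantel-Haenszel strata are not stated.

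**What to change.** - **Phase 2 proportions:** report the difference between doses stratified by age group, with Mantel-Haenszel weights and stratified Newcombe limits. Leave the dose-selection table on observed percentages.
- **Phase 2 titres:** take the GMT and GMFR ratios from a linear model on log titre with dose and age group as terms.
- **Solicited adverse events:** state the Cochran-Mantel-Haenszel strata as age group in Phase 2, and age group and province in Phase 3. Keep Fisher's exact test for sparse events.

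The cost is a few sentences in the SAPs and minor programming, with no new data and no change in sample size. The Phase 2 items belong in the interim SAP before group-level unblinding. If those results have already been seen, add them as a labelled supplementary analysis beside the planned intervals.
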